5.2.6. Endpoint Selection for Analysis

Unless mentioned otherwise all clinical endpoints will be analyzed based on the assessment of the CSAC, supported by the algorithmic approach as explained above. Cases that are adjudicated as not a case by the CSAC are excluded from the analysis. Furthermore, for any symptomatic case to be included in this analysis there needs to be at least one SARS-CoV-2 positive RT-PCR or molecular test result from any available respiratory tract sample (e.g., nasal swab sample, sputum sample, throat swab sample, saliva sample) confirmed by the central laboratory.

Supplementary analysis will include:

- An analysis based on the algorithmic classification as assigned above (limiting to centrally confirmed cases)
- An analysis based on any documented positive PCR irrespective of the source (central confirmation, local site, Covance, external to the study) according to the accepted/reviewed severity and onset date by the CSAC
- An analysis will be done including suspected cases adjudicated by the CSAC.

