- **Resolution of an episode:** Resolution of the COVID-19 episode is defined as having 2 consecutive SARS-CoV-2 negative nasal swabs and 2 consecutive days with no COVID-19-related signs or symptoms. [The date taken will be the first of the 2 consecutive negative swabs, OR the first day with no COVID-19 related signs or symptoms, whichever comes last. For this determination, all sources of information will be used (eCOA, eCRF or an AE linked to COVID-19). In case of missing days, it will depend on if those are before or after the first day of the two consecutive SARS-CoV-2 negative nasal swabs. If before days with missing data have no consequence. If after, it is assumed that if days with missing data are after a day with no symptoms, the subsequent days also were without symptoms. If days with missing data are after a Day with symptoms, the assumption depends on the data of subsequent Days. If there are no more than 2 Days without data and the next Day does have (at least mild) symptoms, the missing days will be assumed to also have had symptoms. In all other cases it will be assumed that days with missing data were without symptoms and the rule to determine the resolution of symptoms will be applied.]
- **Molecularly confirmed case:** Events for which at least one SARS-CoV-2 PCR positive test was obtained by the nasal swab PCR test.
- **A suspected COVID-19 case** is a case which meets any of the symptomatic COVID-19 definitions according to the CSAC without a documented PCR positive result (any source) or a positive serology test.

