5.2.5. Asymptomatic or Undetected SARS-COV-2 Infection

5.2.5.1. Definition

If a participant does not fulfil the criteria for suspected COVID-19 based on signs and symptoms which would classify them as mild, moderate, or severe by the definitions,

AND

has a SARS-CoV-2 positive RT-PCR or molecular test result from any available respiratory tract sample (e.g., nasal swab sample, sputum sample, throat swab sample, saliva sample) or other sample

OR

determined by seropositivity for the SARS-CoV-2 N protein,

then, the participant will be considered to have experienced asymptomatic or undetected COVID-19.

A positive RT-PCR for SARS-CoV-2 will need to be captured in the eCRF.

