 - Seroconverted cases reviewed by the CSAC as symptomatic will be classified as **serologically confirmed COVID-19** (by N-serology) and evaluated according to the accepted/reviewed severity and onset date.
 - PCR positive cases reviewed by the CSAC as symptomatic will be classified and evaluated according to the accepted/reviewed severity and onset date.

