5.3. Exploratory Endpoint(s) Analysis

5.3.1. Definition of Endpoints and Estimands

5.3.1.1. Exploratory endpoint(s)

The exploratory endpoint(s) is defined as a COVID-19 case meeting case definitions, as defined in Sections 5.2.4 and 5.2.5, with onset at least 14 days post last vaccination.

Estimand 1:

What is the relative vaccine efficacy against moderate to severe/critical COVID-19 of Ad26.COV2.S booster vaccination at different dose levels within and between cohorts in adults ≥ 18 years with or without comorbidities associated with increased risk of progression to severe COVID-19?

Population: Adults ≥ 18 years with or without comorbidities associated with increased risk of progression to severe COVID-19 cases and who previously received primary vaccination with Ad26.COV2.S or BNT162b2 and subsequently received Ad26.COV2.S boost on the study.

Endpoint: Molecularly confirmed symptomatic moderate to severe/critical COVID-19 Omicron infections with onset ≥ 14 days after last study vaccination.

Intercurrent Events: Other COVID-19 vaccines.

Data handling for estimators: Cases will be counted from the day after last Ad26.COV2.S vaccination until and including the last available timepoint in the database. Participants with a SARS-CoV-2 infection (symptomatic or asymptomatic) prior to 14 days post last study vaccination will be excluded from the risk set.

A subject will be censored:

- If no event of interest to the analysis was experienced during the considered observation period
- On the date of receipt of another authorized/approved COVID-19 vaccine outside of the study, the date of study discontinuation or the last available date (data lock point), whichever occurred first.

The above defined Estimand approach will be used for following interventions and summary measures:

Estimand	Interventions	Summary Measures ¹
Within each Cohort: (Cohort 1 and 2 separately)		
Estimand 1.1	Ad26.COV2.S 5×10^{10} vp and Ad26.COV2.S 1×10^{10} vp	Relative VE = 100 x (1-hazard ratio of Ad26.COV2.S 5×10^{10} vp / Ad26.COV2.S 1×10^{10} vp)%
Estimand 1.2	Ad26.COV2.S 2.5×10^{10} vp and Ad26.COV2.S 1×10^{10} vp	Relative VE = 100 x (1-hazard ratio of incidence Ad26.COV2.S 2.5×10^{10} vp / Ad26.COV2.S 1×10^{10} vp)%
Between Cohorts:		
Estimand 1.3	Ad26.COV2.S 5×10^{10} vp (Cohort 1) and Ad26.COV2.S 5×10^{10} vp (Cohort 2)	Relative VE = 100 x (1-hazard ratio of Cohort 1 Ad26.COV2.S 5×10^{10} vp / Cohort 2 Ad26.COV2.S 5×10^{10} vp)%

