5.4. Other Analyses

5.4.1. Definition of Subgroups

Selected descriptive statistics will be provided by vaccination dose groups in each cohort for the following subgroups:

- sex
- age group (18 - ≤ 59 & ≥ 60 years)
- presence of baseline comorbidity (yes/no)
- sites
- higher geographical region (West; Midwest; Northeast and South): Categorization of regions by pooling of US states as are described in [Table 3](#) (based on U.S. Department of Commerce Economics and Statistics Administration U.S. Census Bureau).

Table 3: Geographical Regions

CTMS Site #	City, State	Region
PPD	North Charleston, SC	South
	Peoria, IL	Midwest
	Houston, TX	South
	Rochester, NY	Northeast
	Lenexa, KS	Midwest
	Lexington, KY	South
	Long Beach, CA	West
	Mount Pleasant, SC	South
	Tucson, AZ	West
	Phoenix, AZ	West
	Metairie, LA	South
	Hallandale Beach, FL	South
	Hollywood, FL	South
	Boston, MA	Northeast
	The Villages, FL	South
	Orlando, FL	South
	Anaheim, CA	West
	West Jordan, UT	West
	N. Hollywood, CA	West
	Denver, CO	West
	Anderson, SC	South
	Boston, MA	Northeast

Analysis Methods:

Descriptive analyses/summary will be provided for PPE analysis set for each cohort by dose groups. These analyses may include but are not limited to:

- The number and percentage of severity of SARS-CoV-2 COVID-19 cases
- Number of events and follow-up time for SARS-CoV-2 COVID-19 cases by subgroups
- Based on availability of the data, for COVID-19 requiring medical intervention/ hospitalization, a summary table will be provided by type of intervention (as indicated by the adjudicators, if available) with onset at least 14 days post last vaccination. A severity adjusted analysis will be done on the medical intervention endpoint (such as composite endpoint of hospitalization, ICU admission, mechanical ventilation, and ECMO, linked to objective measures such as decreased oxygenation, X-ray or CT findings

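### For Estimands 1–4, symptomatic cases confirmed only by N-serology are events in none of the four analyses in supplemental SAP 5.2.6, while symptomatic cases with no laboratory evidence are events in one

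*SAP*

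**What the plan says.** All section numbers refer to the supplemental SAP on exploratory efficacy.

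- **Objectives (1.1).** The rVE objectives cover symptomatic and asymptomatic infection confirmed by serology, by molecular testing, or by both.
- **Classification (5.2.5.2).** "Seroconverted cases reviewed by the CSAC as symptomatic will be classified as" serologically confirmed COVID-19, and they are to be evaluated by the accepted or reviewed severity and onset date.
- **Main analysis (5.2.6).** The rule is that "for any symptomatic case to be included in this analysis there needs to be at least one SARS-CoV-2 positive RT-PCR or molecular test result", confirmed by the central laboratory. The endpoints of Estimands 1–4 match this; Estimand 1, for example, takes "Molecularly confirmed symptomatic moderate to severe/critical COVID-19 Omicron infections".
- **First supplementary analysis (5.2.6).** "An analysis based on the algorithmic classification as assigned above (limiting to centrally confirmed cases".
- **Second supplementary analysis (5.2.6).** It takes any documented positive PCR, whatever its source, with severity and onset as adjudicated.
- **Third supplementary analysis (5.2.6).** "An analysis will be done including suspected cases adjudicated by the CSAC". Section 5.2.2 defines a suspected case as symptomatic according to the CSAC "without a documented PCR positive result (any source) or a positive serology test".
- **Asymptomatic/undetected infection (5.2.5.1, Estimand 5).** The class accepts a positive PCR or N-seropositivity. It leaves out participants with signs and symptoms "which would classify them as mild, moderate, or severe by the definitions".

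**The concern.** The supplementary set exists to show what happens when confirmation is relaxed. As written, it relaxes confirmation all the way to cases with no laboratory evidence and passes over cases with N-serology, which the SAP itself accepts as evidence of infection for Estimand 5. The order of evidence is reversed.

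There is also an internal conflict. Section 5.2.5.2 promises to evaluate these cases by severity and onset, and the objectives include serologically confirmed symptomatic infection, yet no analysis listed in 5.2.6 does this for Estimands 1–4. The censoring rules under each estimand do not end follow-up at such an infection, so in the main analysis the participant goes on contributing event-free time. Section 5.3.2 allows an analysis from 6 cases upward, so a handful of cases could matter in a sparse comparison. Whether there are that many is not known.

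**Working it through.** No sample-size or error-rate figure bears on this point. The check compares case types with inclusion rules.

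**Step 1: Estimands 1–4.** Each row is a case that the CSAC judges symptomatic. The columns are the four analyses in 5.2.6.

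| Evidence of infection | Main | Suppl. 1 | Suppl. 2 | Suppl. 3 | Total |
|---|---|---|---|---|---|
| Centrally confirmed PCR | yes | yes | yes | yes | 4 of 4 |
| PCR from another source only | no | no | yes | no | 1 of 4 |
| N-serology only, no positive PCR | no | no | no | no | 0 of 4 |
| Neither PCR nor serology | no | no | no | yes | 1 of 4 |

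The third row depends on how the suspected-case definition is read. If it were read to admit serology-positive cases, that row would become 1 of 4.

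**Step 2: Estimand 5 for the N-serology-only case.**

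- Main analysis: the CSAC finds it symptomatic, so 5.2.5.1 no longer admits it and 5.2.5.2 moves it to serologically confirmed COVID-19. With Step 1, it is an event in no estimand.
- First supplementary analysis: this uses the algorithm's class. Sections 5.2.1 and 5.2.5.2 let the algorithm label a seroconverter asymptomatic/undetected first and look for symptoms afterwards. The case can therefore be an Estimand 5 event, unless the limit to centrally confirmed cases also governs serology. Section 5.2.6 attaches central confirmation to PCR or molecular results in symptomatic cases and does not say how it applies to N-serology.

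**Step 3: the minor point.** The FDA-harmonized list in 5.2.4.4 has 17 items. Against the lists in 5.2.4.1 to 5.2.4.3:

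- 14 are in the mild list: fever, cough, chills, sore throat, fatigue, muscle aches, headache, smell, taste, chest congestion, runny nose, diarrhea, vomiting, nausea.
- 1 is only in the moderate list: shortness of breath.
- 2 are in no severity list: nasal congestion, joint aches/pains.
- 14 + 1 + 2 = 17.

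For a PCR-positive case with only those two symptoms, the result depends on which passages are programmed:

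| | 5.2.5.1: asymptomatic unless mild, moderate or severe | 5.2.5.2: asymptomatic only without signs or symptoms |
|---|---|---|
| 5.2.4.4: FDA definition stands alone | Estimands 4 and 5 | Estimand 4 |
| 5.2.4: symptomatic means at least mild | Estimand 5 | neither |

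**The case against.** **The suspected-case wording can be stretched.** It can be read so that serology-positive cases qualify, and 5.2.6 does not say that its list of supplementary analyses is closed. Output details are left to data presentation specifications that are not at hand. This stands as a possibility. It is the less natural reading, and a single sentence would settle it if it is what was meant.

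**Requiring PCR is legitimate.** A reader might infer that the main analysis is wrong to demand molecular confirmation. The documents do not support that. It is a defensible choice and is not disputed here.

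**These cases are not shut out of every analysis.** A reader might infer that they enter no rVE analysis at all. That goes too far. In the algorithm-based analysis they can still be Estimand 5 events, and extending central confirmation to serology would also drop every truly asymptomatic seroconverter without a PCR from that analysis. The descriptive summaries in 5.4.1, such as "The number and percentage of severity of SARS-CoV-2 COVID-19 cases", may show them too, although those give no rVE.

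**The minor point is easily overstated.** A reader might infer that one infection is bound to be counted as symptomatic in Estimand 4 and asymptomatic in Estimand 5. That outcome needs both the at-least-mild wording of 5.2.4 and the no-symptoms wording of 5.2.5.2 to be set aside. Overlap between estimands is also no error in itself: a moderate case can count in Estimands 1, 2 and 4. Section 5.2 makes the CSAC's ruling final for the main analysis. What remains is that four passages disagree. Section 5.2.3 refers to the protocol for the severity definitions, so the item count holds for the SAP's own lists only.

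**Conclusion.** The point holds for Estimands 1–4. On the natural reading of 5.2.2, a symptomatic case confirmed only by N-serology is an event in 0 of the 4 analyses, against 1 of 4 for a symptomatic case with no laboratory evidence. In the main analysis it is an event in none of the five estimands, contrary to the objectives and to 5.2.5.2. Under Estimand 5 in the algorithm-based analysis, its status is open.

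The number of such cases cannot be derived from the document, so neither the direction nor the size of any effect on rVE can be stated. The symptom-list conflict is a minor reconciliation; its effect is probably small and falls mainly on the algorithm-based analysis. Both points concern exploratory rVE only and leave the primary immunogenicity conclusions untouched.

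**What to change.** 1. In 5.2.6, widen the third supplementary analysis to take CSAC-adjudicated serologically confirmed symptomatic cases as well as suspected cases, by adjudicated severity and onset. Keep the PCR-confirmed analysis as main. In the same place, state whether the limit to centrally confirmed cases in the first supplementary analysis applies to N-serology.
2. In 5.2.5.1, add one sentence: a case that meets 5.2.4.4 and has the molecular confirmation required in the analysis concerned is not asymptomatic/undetected and counts in Estimand 4. Tying the sentence to each analysis's own confirmation rule keeps a case from dropping out of both estimands.

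The cost is SAP wording, a small change to derivation code, one wider supplementary table and perhaps slightly fewer Estimand 5 events. Cases known only by serology have no positive swab to sequence, so their variant would rest on the presumption in 5.3.2 that Omicron dominated, as it already does for suspected cases.

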5.3. Exploratory Endpoint(s) Analysis

5.3.1. Definition of Endpoints and Estimands

5.3.1.1. Exploratory endpoint(s)

The exploratory endpoint(s) is defined as a COVID-19 case meeting case definitions, as defined in Sections 5.2.4 and 5.2.5, with onset at least 14 days post last vaccination.

Estimand 1:

What is the relative vaccine efficacy against moderate to severe/critical COVID-19 of Ad26.COV2.S booster vaccination at different dose levels within and between cohorts in adults ≥ 18 years with or without comorbidities associated with increased risk of progression to severe COVID-19?

Population: Adults ≥ 18 years with or without comorbidities associated with increased risk of progression to severe COVID-19 cases and who previously received primary vaccination with Ad26.COV2.S or BNT162b2 and subsequently received Ad26.COV2.S boost on the study.

Endpoint: Molecularly confirmed symptomatic moderate to severe/critical COVID-19 Omicron infections with onset ≥ 14 days after last study vaccination.

Intercurrent Events: Other COVID-19 vaccines.

Data handling for estimators: Cases will be counted from the day after last Ad26.COV2.S vaccination until and including the last available timepoint in the database. Participants with a SARS-CoV-2 infection (symptomatic or asymptomatic) prior to 14 days post last study vaccination will be excluded from the risk set.

A subject will be censored:

- If no event of interest to the analysis was experienced during the considered observation period
- On the date of receipt of another authorized/approved COVID-19 vaccine outside of the study, the date of study discontinuation or the last available date (data lock point), whichever occurred first.

The above defined Estimand approach will be used for following interventions and summary measures:

Estimand	Interventions	Summary Measures ¹
Within each Cohort: (Cohort 1 and 2 separately)		
Estimand 1.1	Ad26.COV2.S 5×10^{10} vp and Ad26.COV2.S 1×10^{10} vp	Relative VE = 100 x (1-hazard ratio of Ad26.COV2.S 5×10^{10} vp / Ad26.COV2.S 1×10^{10} vp)%
Estimand 1.2	Ad26.COV2.S 2.5×10^{10} vp and Ad26.COV2.S 1×10^{10} vp	Relative VE = 100 x (1-hazard ratio of incidence Ad26.COV2.S 2.5×10^{10} vp / Ad26.COV2.S 1×10^{10} vp)%
Between Cohorts:		
Estimand 1.3	Ad26.COV2.S 5×10^{10} vp (Cohort 1) and Ad26.COV2.S 5×10^{10} vp (Cohort 2)	Relative VE = 100 x (1-hazard ratio of Cohort 1 Ad26.COV2.S 5×10^{10} vp / Cohort 2 Ad26.COV2.S 5×10^{10} vp)%
Estimand 1.4	Ad26.COV2.S 2.5×10^{10} vp (Cohort 1) and Ad26.COV2.S 2.5×10^{10} vp (Cohort 2)	Relative VE = 100 x (1-hazard ratio of Cohort 1 Ad26.COV2.S 2.5×10^{10} vp / Cohort 2 Ad26.COV2.S 2.5×10^{10} vp)%
Estimand 1.5	Ad26.COV2.S 1×10^{10} vp (Cohort 1) and Ad26.COV2.S 1×10^{10} vp (Cohort 2)	Relative VE = 100 x (1-hazard ratio of Cohort 1 Ad26.COV2.S 1×10^{10} vp / Cohort 2 Ad26.COV2.S 1×10^{10} vp)%

¹Relative VE and associated 95% CI will be calculated from Cox Proportional hazards model.

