5. STATISTICAL ANALYSES

5.1. General Considerations

Unless otherwise indicated, all analyses will pool data across ages and independent of comorbidity status for evaluation without stratification.

The rVE analysis of booster vaccination with Ad26.COV2.S will include efficacy data collected during the entire study, i.e., with an onset date of the event (or censoring date) up to the database cut-off or until study discontinuation of the participant.

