5.1.2. Phase Definitions

For phase definitions refer to main SAP (EDMS RIM-462169); Section 5.1.2.

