5.3.2. Analysis Method

Exploratory analysis will be done on the PPE analysis set including only baseline seronegative subjects. The analysis will focus on the Omicron variant, as this is presumed to be the dominant variant during the observation period.

Analysis will be performed if there are at least 6 cases available for the analysis of interest.

i) Calendar-Based Time Scale Method:

For the exploratory efficacy endpoints, follow-up time will be expressed on a calendar time scale, and is defined as time since study start (i.e., 08 August 2021) to adjust for changing incidence over time. Follow-up time will begin on the date of administration of the first dose of Janssen COVID-19 vaccine (within study COV2008), expressed on a calendar time scale as time since study start,

although follow-up time and events occurring within 14 days post vaccination with first dose of Janssen COVID-19 vaccine will be ignored.

The follow-up time is the time to first occurrence of moderate to severe disease, with an onset at any time at least 14 days post vaccination of previously received Janssen COVID-19 vaccine. An individual will be censored at i) the date of receipt of another authorized/approved COVID-19 vaccine, including the Janssen COVID-19 vaccine if received outside of the study, ii) the date of study discontinuation, or iii) the last available date, whichever occurred first.

Vaccine efficacy will be summarized by relative vaccine efficacy measures and the associated 95% confidence intervals (CI) using time-dependent Cox Proportional hazards models , stratified by the following factors to account for i) changing incidence over calendar time, ii) potential confounding by age [18 - <60 years (as reference category), ≥ 60 years], co-morbidities [Y/N (as a reference category)] and geographical region in which the site is located (cf. Section 5.4.1).

One model will be fit estimating VE under the assumption of constant relative vaccine efficacy (Fintzi et al, 2020), comparing:

- Within each Cohort, from higher dose levels (i.e. Ad26.COV2.S 5×10^{10} vp and 2.5×10^{10} vp) to lower dose level (Ad26.COV2.S 1×10^{10} vp).
- Heterologous booster (Cohort 2) to homologous booster (Cohort 1) vaccination at same dose level.

Models that do not converge will be omitted and reported as non-convergent. The method for tabulating relative VE and 95% CI will be detailed in DPS.

Estimand 2:

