5.8.2. Planned Analysis

The primary and final analyses of Cohort 1 may be performed before the analyses of Cohort 2.

The primary analysis of safety and immunogenicity in Cohort 1 or Cohort 2 will be performed when all evaluable participants in the respective cohort have completed the visit that takes place 28 days after study vaccination or discontinued earlier. The analysis will include immunogenicity data (VNA, S-ELISA, N-serology) for all evaluable participants through Day 15, and all available safety data. The sponsor will be unblinded for the respective cohort at the time of this primary analysis, but the blind will be maintained at the participant and study site level up to study end.

The final analysis in Cohort 1 or Cohort 2 will be performed when all included participants in the respective cohort have completed their last visit or discontinued earlier.

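### The relative vaccine efficacy censoring rules omit study completion and conflict with other text on when a completer's follow-up ends; read literally, they can bias the between-cohort comparison if the cohorts finish at different times

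*SAP*

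**What the plan says.** **Estimand text.** Section 5.3.1.1 of the supplemental SAP (Estimand 1) has two censoring bullets. The first applies "If no event of interest to the analysis was experienced during the considered observation period", and that period is not defined there. The second sets the date: receipt of another COVID-19 vaccine outside the study, "the date of study discontinuation or the last available date (data lock point), whichever occurred first". The same bullets are repeated for Estimands 2 to 5, which are printed under Section 5.3.2.

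**General text.** Section 5.1 includes efficacy data "with an onset date of the event (or censoring date) up to the database cut-off or until study discontinuation of the participant". Section 5.1.3 names the same two limits.

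**Method text.** Section 5.3.2 restates the rule for the calendar-time Cox model. After off-study vaccination it lists "ii) the date of study discontinuation, or iii) the last available date, whichever occurred first", with no mention of data lock.

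**Phases.** Section 5.1.2 of the supplement says: "For phase definitions refer to main SAP (EDMS RIM-462169); Section 5.1.2". Table 1 in that main SAP section ends follow-up at the earliest of last contact (early discontinuation), database cut-off (interim analysis) and last visit.

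**Cohort timing.** Main SAP Section 5.8.2 states: "The primary and final analyses of Cohort 1 may be performed before the analyses of Cohort 2". It places the final analysis of a cohort at the point when all its included participants "have completed their last visit or discontinued earlier".

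**The concern.** No version of the rVE rule names completion, the last visit or the last contact. Nor does discontinuation clearly cover completers: main SAP Sections 5.6.2.3 and 5.8.2 both treat completing and discontinuing as different outcomes. If the last available date is the data lock point, a completer stays in the risk set after surveillance has stopped.

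An event can hardly arise in that time. Section 5.2.6 requires a positive molecular test confirmed by the central laboratory before a symptomatic case enters the main analysis. The extra time adds to the denominator but in practice not to the events. This matters mainly for the PCR-confirmed Estimands 1 to 4.

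The calendar time scale does not remove the problem. If one cohort finishes first, its completers are compared, on the same dates, with participants in the other cohort who can still become cases. The exposed contrasts are the between-cohort ones (Estimands x.3 to x.5). The follow-up-time tables of Section 5.4.1 would be diluted as well, and Kaplan-Meier curves (Section 5.3.3) built on the same end date would gain a flat tail.

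**Working it through.** The SAP gives no case numbers, power or cohort dates for the rVE analysis, so there is no figure to reproduce. The check has a textual part and a conditional calculation.

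**Step 1: end of risk time for a completer, by section**

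| Place | End of risk time |
|---|---|
| Suppl. 5.3.1.1 and Estimands 2 to 5 | Data lock point |
| Suppl. 5.1 and 5.1.3 | Database cut-off |
| Suppl. 5.3.2, method paragraph | Last available date, not defined |
| Main 5.1.2, adopted by suppl. 5.1.2 | Last visit |

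These do not agree.

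**Step 2: inputs for the size**

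From the SAP: calendar time scale, follow-up within 14 days of the booster ignored, and Cohort 2 compared with Cohort 1 at the same dose.

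Assumed, because the SAP does not give them: uniform enrolment over 3 months per cohort; Cohort 2 starting L months after Cohort 1; surveillance of F = 12 or 6 months (Section 1.1 lists immune sampling to 1 year, but no surveillance length is stated); lock at the last participant's last visit; no events recorded after a participant's own last visit; true HR = 1.

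**Step 3: formula**

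For cohort k at calendar time t, let Rk(t) be the fraction the rule keeps in the risk set, Sk(t) the fraction truly under surveillance and h(t) the hazard. For rare events in large samples, the Cox HR r (Cohort 2/Cohort 1) solves

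∫ { S2·h − (S1 + S2)·h · r·R2 / (R1 + r·R2) } dt = 0.

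Censoring at the last visit makes Rk = Sk, and r = 1 solves it exactly.

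**Step 4: hand check**

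Suppose everyone in a cohort enrols on one day and the hazard is constant. While both cohorts are in the risk set, Cohort 2 has F − 0.5 months that can yield events and Cohort 1 has F − L − 0.5. Under lock censoring both stay in the risk set throughout, so r = (F − 0.5)/(F − L − 0.5).

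- F = 12: 11.5/10.5 = 1.10, 11.5/9.5 = 1.21, 11.5/8.5 = 1.35 for L = 1, 2, 3.
- F = 6: 5.5/4.5 = 1.22, 5.5/3.5 = 1.57, 5.5/2.5 = 2.20.

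**Step 5: results with 3-month enrolment, lock censoring, true HR = 1**

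The wave hazard is 1 + 10·exp(−(t − 5)²/2), with t in months from the start of Cohort 1.

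| Lag L (months) | F = 12, constant | F = 12, early wave | F = 6, constant | F = 6, early wave |
|---|---|---|---|---|
| 0 | 1.00 | 1.00 | 1.00 | 1.00 |
| 1 | 1.09 | 1.03 | 1.21 | 1.06 |
| 2 | 1.20 | 1.06 | 1.51 | 1.11 |
| 3 | 1.34 | 1.12 | 1.99 | 1.21 |

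Censoring at the last visit gives 1.000 in every cell. With L = 0 the result stays 1.000 even if lock falls 3 months after the last visit; the same logic covers dose arms that enrol in parallel within a cohort. If Cohort 2 enrolled first, the HRs are the reciprocals, for example 1/1.337 = 0.75. With a true HR of 0.70, F = 12, L = 3 and a constant hazard, the fitted HR is 0.938, so an rVE of 30% would appear as about 6%.

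**Step 6: dilution of follow-up time**

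Under the same assumptions, with no early exits, lock is at L + 3 + F. Mean completion is at 1.5 + F in Cohort 1 and L + 1.5 + F in Cohort 2. Mean unobserved time is then L + 1.5 and 1.5 months. With F = 12 and L = 3, observed time is 12 − 0.5 = 11.5 months. Incidence would be multiplied by 11.5/(11.5 + 4.5) = 0.72 in Cohort 1 and 11.5/(11.5 + 1.5) = 0.88 in Cohort 2.

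**The case against.** The strongest reply is that the plan, read as a whole, already ends follow-up at the last visit. Section 5.3.2 is the operative method and speaks of an individual being censored at the last available date, which for a completer could be that person's own last date. The adopted phase table ends at the last visit, the main SAP's whole-study period ends per participant, and the first censoring bullet refers to an observation period. This stands to one extent: a reader might infer that the plan definitely keeps completers at risk until lock, and the documents do not settle that. It does not remove the conflict, because the rVE rule never invokes the phases and all five estimands state data lock outright.

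A reader might also infer that the heterologous-versus-homologous rVE is certainly biased against the later cohort. That is not supported either. Section 5.8.2 only permits Cohort 1 to be analysed first; it does not say that Cohort 1 enrolled or finished first. With equal timing there is no bias.

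The constant-hazard figures are the high end. The calendar scale was chosen because incidence changes over time, and an early wave cuts the 12-month range to 1.03 to 1.12. Precision is also limited: analyses may run on 6 cases, and a 3/3 split gives a 95% CI factor of exp(1.96 × √(2/3)), about 5 in each direction. That can hide the bias in sparse contrasts, but the SAP gives no expected case numbers, and the bias does not shrink as cases accrue.

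**Conclusion.** The point holds as a conflict in the stated end of risk time. The estimand rules and Sections 5.1 and 5.1.3 leave out completion, and the estimands define the last available date as data lock. This disagrees with the adopted last-visit end of follow-up and is not matched by the wording of Section 5.3.2.

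The consequence is conditional. Diluted follow-up time follows whenever the literal rule is used. Bias in Estimands x.3 to x.5 also needs the cohorts to complete at different calendar times. For an assumed Cohort 2 lag of 1 to 3 months and a true HR of 1, the Cohort 2/Cohort 1 HR is about 1.03 to 1.34 (12 months of surveillance) or 1.06 to 1.99 (6 months). The estimand tables define the ratio as Cohort 1/Cohort 2, whereas Section 5.3.2 compares Cohort 2 with Cohort 1, so the sign of any shift in rVE also depends on which is used. Within-cohort dose contrasts are little affected if the arms enrol in parallel.

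These analyses are exploratory and the confirmatory non-inferiority tests do not use this rule. It is a worthwhile, cheap correction, not a threat to the trial's main conclusions.

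**What to change.** In every estimand and in Sections 5.1, 5.1.3 and 5.3.2, censor at the earliest of: off-study COVID-19 vaccination; study discontinuation; study completion, meaning the participant's last visit or last surveillance contact; and data cut-off. Replace the undefined last available date with this list throughout. Use the same end date for the Kaplan-Meier curves in Section 5.3.3 and the events and follow-up-time tables in Section 5.4.1.

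The cost is one phrase repeated in each rule and one derived date per participant. No new data are needed.
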